3.2 Sample size

Sample sizes are chosen based on feasibility and precision because no hypothesis is tested in this study. The primary endpoint is the proportion of subjects with serum HBV DNA <20 IU/mL of TDF in multiple NAs treatment failure patients at Week 144.

To decide the number of subjects for analysis, some precision calculations have been performed. From our historical data, we hypothesize that the proportion of subjects with serum HBV DNA <20 IU/mL in multiple NAs treatment failure patients treated with TDF at Week 144 was 80%. A sample size of 170 patients will allow us to estimate the confidence interval of the incidence with a margin of error at 6% (range from 74-86%). Assuming a dropout rate of 15 per cent during a 144 week period, the number of patients required overall is estimated to be 200.

4. ANALYSIS SET

• Modified Intent-to-treat (mITT) Population

The mITT population is defined as all recruited subjects who receive at least one dose of study medication.

• Per Protocol (PP) population

The PP population will consist of subjects in the mITT population who have no major protocol deviations that impact the safety and efficacy evaluation.

• Safety Analysis (SA) population

The SA population is defined as all subjects who receive at least one dose of study medication and have at least one post baseline safety assessment.

All efficacy endpoints will be analyzed using the mITT and PP population. All safety endpoints will be analyzed using the SA population according to the actual treatment they received.

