- Subjects have HBV DNA ≥200IU/ml at week 48 and afterwards have ≤ 1 log10 IU/ml decrease in HBV DNA at two consecutive tests, confirmed by a third visit(additional visit) at least one month apart.

Meanwhile, subjects to be received rescue therapy must have investigational product (IP) compliance > 80% in the last regular visits period (usually 12 weeks).

Another NA(s) without cross-resistance (eg. LAM, LdT, or ETV) will be added, the choice to be decided by the investigator.

Additional Visit: During the treatment phase, subjects who do not achieve satisfied response to TDF (eg.experience virological breakthrough or HBV DNA level does not continue to decline,) need to perform another HBV DNA test at an additional visit at least one month apart. Before rescue treatment initiation, serum sample should be collected for resistance testing.

During the treatment phase, patients that have evidence of HBsAg loss or seroconversion and HBeAg loss/seroconversion (for baseline HBeAg positive subjects) and HBV DNA < 20 IU/ml at any two consecutive visits at least 3 months apart will enter a non-treatment observational arm of the study, and will be followed up until the end of the study according to protocol-defined assessments and procedures. Study treatment should be stopped within 15 days of the result confirming that the subject meets the criteria.

If a patient in the non-treatment observational arm subsequently develops HBV DNA  $\geq$ 20 IU/ml, HBsAg re-emerges, and ALT > 1.5 ULN, they will be eligible to be re-treated with TDF up to week 144 of the study. Once the treatment is restarted, the patients should be followed at least every 12 weeks as protocol defined and the data will be entered as the corresponding scheduled visit.

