# 5. STUDY TREATMENTS

## 5.1. Investigational Product and Other Study Treatment

Tenofovir disoproxil fumarate (9-[(R)-2-[[bis[[(isopropoxy-carbonyl) oxy] methoxy] phosphinyl] methoxy] propyl] adenine fumarate (1:1)); GS4331-05) is an oral pro-drug

(bisPOC-PMPA) of TFV (PMPA), an acyclic nucleoside phosphonate (nucleotide) analogue of adenosine 5'-monophosphate. TDF has demonstrated antiviral activity against HBV and HIV and is indicated for use in combination with other antiretroviral agents in the treatment of HIV infection.

Tenofovir disoproxil fumarate tablets are white, almond-shaped, film-coated tablets containing 300 mg of TDF, debossed with "GILEAD" and "4331" on one side of the tablet. Each tablet contains the following inactive ingredients: microcrystalline cellulose, lactose monohydrate, pregelatinised starch, croscarmellose sodium, and magnesium stearate. The tablets are film coated with Opadry II White 32K18425.

TDF are packaged in white, high-density polyethylene bottles with a white child resistant cap. There are 30 tablets per bottle. Each bottle also contains silica gel canister(s) to protect the product from humidity and fibre packing to protect the product during handling and shipping.

For subjects who do not achieve satisfied response to TDF will add another drug without cross resistant to TDF including LAM (Heptodin, GlaxoSmithKline, 100mg QD), ETV (Baraclude, Bristol-Myers Squibb,0.5mg QD) and LdT(Sebivo,Novartis,600mg QD). Investigator will make the decision for the drug selection.

The contents of the label will be in accordance with all applicable regulatory requirements.

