## 5.2. Treatment Assignment

This is an open label, single arm study.

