#### 8.3.5.2. Safety analyses

Clinical safety observations will include: extent of exposure information, AEs, deaths, laboratory abnormalities and withdrawals from study.

Extent of exposure to study drug data will be generated from the study drug administration page of CRF. Exposure data will be summarised by treatment group.

Adverse events will be assigned preferred terms and categorized into body systems according to the MedDRA classification of the World Health Organisation terminology. The proportion of subjects who experienced AEs will be calculated by dividing the number of subjects who experienced the AE during the treatment period by the number of subjects evaluable for safety analysis. Adverse events will be summarised by treatment group, and by body system and event within each body system. The following summaries of AEs will be provided:

- All AEs.
- All treatment related AEs.
- All SAEs.
- All treatment related SAEs.
- All AEs leading to permanent discontinuation of study drug.
- All AEs leading to permanent discontinuation from the study.

• All AEs that caused a change in dose or temporary interruption of study drug.

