7.5.1 Adverse events

AEs will be classified into standardized medical terminology from the verbatim description (investigator term) using the Medical Dictionary for Regulatory Activities (MedDRA). Verbatim description and MedDRA level terms, including the system organ class, preferred term, and lower level term, for all AEs will be presented in the data listings. In table summaries, the denominator for percentages will be the number of subjects in the treatment group within the safety analysis population. AEs are coded according to (MedDRA) version 17.0.

TEAE is defined as AE occurred on or after the first dose date of study drug. TEAEs will be presented by system organ class and preferred term. The subject level incidence is only one occurrence of a preferred term/system organ class per subject. If a subject reports multiple AEs under the same preferred term, then the count of subject level incidences for that preferred term will only be incremented by one. If a subject reports multiple AEs under the same system organ class, then the count of subject level incidences for that system organ class will also only be incremented by one. System organ classes will be presented in descending order of total frequency of subject level occurrences. Within each system organ class, preferred terms are presented in the same descending order of total frequency of subject level occurrences.

The following summaries of AEs will be provided:

- All AEs.
- All TEAEs.
- All treatment related TEAEs.
- All serious TEAEs.
- All non-serious TEAEs.
- All treatment related serious TEAEs.
- All TEAEs leading to permanent discontinuation of study drug.
- All TEAEs leading to permanent discontinuation from the study.
- All TEAEs that caused a change in dose or temporary interruption of study drug.

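### The planned safety tables pool events on TDF alone, on TDF plus an added NA, and off treatment, so they do not show the safety of TDF alone

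*SAP*

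**What the plan says.** The study has one arm (Protocol 5.2: "This is an open label, single arm study"), and the safety objective in SAP 2.2 is the safety of TDF after failure of multiple NAs.

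Treatment can nevertheless change within a subject:

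- **Add-on.** Protocol 3.1 says of subjects without a satisfactory response: "Another NA(s) without cross-resistance (eg. LAM, LdT, or ETV) will be added, the choice to be decided by the investigator". Protocol 5.1 repeats this: "For subjects who do not achieve satisfied response to TDF will add another drug without cross resistant to TDF". TDF continues.
- **Off treatment.** Under Protocol 3.1, subjects who meet the HBsAg, HBeAg and HBV DNA criteria stop TDF and are followed in a non-treatment observational arm. Some may later restart TDF.

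The safety rules are these:

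- **Population (SAP 4):** "All safety endpoints will be analyzed using the SA population according to the actual treatment they received".
- **Window (SAP 7.5.1):** "TEAE is defined as AE occurred on or after the first dose date of study drug".
- **Counting (SAP 7.5.1):** "The subject level incidence is only one occurrence of a preferred term/system organ class per subject".
- **Denominator (SAP 7.5.1):** "the denominator for percentages will be the number of subjects in the treatment group within the safety analysis population".
- **Protocol 8.3.5.2** defines the AE proportion differently, dividing "the number of subjects who experienced the AE during the treatment period by the number of subjects evaluable for safety analysis".

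**The concern.** When treatment changes part-way through follow-up, an AE table needs a rule that ties each event to what the subject was taking when it began. The SAP has none. An AE or laboratory abnormality that starts after lamivudine, telbivudine or entecavir is added enters the same column as one that starts on TDF alone. So does an event in a subject who has stopped TDF.

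The stated aim is the safety of TDF. A reader of the final tables could take an event of the added drug, or one that follows stopping treatment, for an event on TDF alone. The summaries most exposed are those with few events, such as serious AEs and Grade 3 or 4 laboratory values.

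**Working it through.** **1. What the tables will contain.** Setting the rules side by side:

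- The AE window opens at the first dose. SAP 7.5.1 gives no closing date and no cut when an NA is added.
- The laboratory rule in SAP 7.5.3 is also open-ended: it counts a qualifying Grade 3 or 4 value at any time after baseline. The same section counts on-treatment hepatitis exacerbations but does not define when a subject is on treatment.
- Exposure in SAP 7.3.3 runs from first to last dose and is not split at add-on.
- Neither document defines a combination group or an off-treatment group for safety.
- In SAP 9, Tables 5.1.1 to 5.1.4.2 and 5.3.3 carry no split by treatment period.

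Together these give one column that holds all three periods.

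**2. SAP window against protocol window.** Protocol 8.3.5.2 limits the numerator to the treatment period; the SAP sets no end. The protocol does not define that period for this purpose. If it means time on drug, the SAP adds the observational time. If it means the scheduled weeks up to 144, as the column heading in Protocol Table 1 suggests, the observational time before week 144 is in both counts. The SAP would then add only later events, such as those found at the early-withdrawal visit 12 weeks off treatment. On either reading the two windows differ.

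**3. Size of the add-on period.** The plan gives no figure for rescue or for exposure on the combination, so there is none to reproduce. Inputs from the documents are 200 enrolled subjects and 144 weeks (Protocol 3.1). The rescued fraction r and the rescue week t are assumptions, with full follow-up for everyone.

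Share of person-time on the combination = r × (144 − t) / 144

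| r | subjects of 200 | t = 108 | t = 60 |
|---|---|---|---|
| 5% | 10 | 0.05 × 36/144 = 1.25% | 0.05 × 84/144 = 2.9% |
| 10% | 20 | 0.10 × 36/144 = 2.5% | 0.10 × 84/144 = 5.8% |
| 15% | 30 | 0.15 × 36/144 = 3.75% | 0.15 × 84/144 = 8.75% |

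In person-weeks this is 10 × 36 = 360 to 30 × 84 = 2,520, out of 200 × 144 = 28,800.

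Rescue can come earlier, because the breakthrough criterion in Protocol 3.1 does not wait for week 48. A wider range is r = 2-20% with t = 24 or 76:

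- lowest: 0.02 × 68/144 = 0.9%
- highest: 0.20 × 120/144 = 16.7%

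**4. Effect on a common AE.** Suppose an AE has 20% incidence over 144 weeks on TDF alone and the added NA doubles its hazard (both assumed). At a constant hazard, a rescued subject's risk is 1 − 0.8^[(t + 2(144 − t))/144]:

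- t = 24: 1 − 0.8^1.833 = 33.6%
- t = 76: 1 − 0.8^1.472 = 28.0%

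Pooled proportion = (1 − r) × 20% + r × (rescued risk):

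- r = 5%: 20.7% (t = 24) and 20.4% (t = 76)
- r = 20%: 22.7% (t = 24) and 21.6% (t = 76)

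The pooled figure moves by 0.4 to 2.7 percentage points from 20%.

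**5. Rare events.** With 200 subjects, one subject is 1/200 = 0.5 percentage points. If only a few subjects have a given serious AE or Grade 4 value, one onset after add-on is a visible part of the count.

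**6. Off-treatment time.** The documents give no rate of entry to the observational arm, so this part cannot be sized.

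**The case against.** The strongest reply is that the pooled column is a legitimate summary. Rescued subjects still take TDF, the objective is not worded as TDF monotherapy, and the protocol permits the add-on. This stands: pooling answers the question of safety under a TDF-based strategy with permitted add-on, and it should stay.

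A second reply is that the information is already planned. Listing 3.1.2 gives medication start and end dates, Listings 4.1.2 and 4.1.3 identify subjects with breakthrough or unsatisfactory response, and Tables 5.1.3.1 and 5.1.3.2 show AEs by relationship to study drug. This stands in part. A careful reader could place a single event before or after the add-on, but no summary does so. The causality tables do not settle it either, because study drug is not confined to TDF: Protocol 5.8 defines overdose for all four drugs, and Protocol 6.3.10 speaks of study drugs in the plural.

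A third reply is that the separate columns will be small and selected. That is true and limits how they can be read.

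Two stronger readings are tempting:

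- **Whole-subject reassignment.** From the phrase about actual treatment, a reader might infer that rescued subjects would be moved entirely to a combination group, taking their earlier TDF-alone events with them. The documents do not support this. There is one arm, no combination group is defined, and no listed output has such a column. References to a treatment group in Protocol 8.3.5.2 and SAP 7.5.1 do not create one. SAP 4 does not say that classification is by subject, and it does not rule out classification at onset.
- **No TDF safety result at all.** A reader might also infer that the plan yields nothing usable on TDF safety. That goes too far, since the pooled summary is valid for the strategy.

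**Conclusion.** The point holds as a limited gap in the reporting of safety. As written, the SAP produces one pooled column covering TDF alone, TDF plus an added NA, and time off treatment. It does not show the safety of TDF alone, and its event window does not match Protocol 8.3.5.2.

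The effect is probably modest. About 1-9% of person-time is on the combination if 5-15% of subjects are rescued between weeks 60 and 108. The wider assumptions give 0.9-16.7%. These figures rest on an assumed rescue rate, assumed timing and complete follow-up; the documents supply none of the three. Overall AE rates would change little. Counts of rare events could change, but by how much cannot be derived from the documents. This is a cheap improvement and not a flaw that undermines the trial.

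**What to change.** In SAP 4 and 7.5, before database lock:

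1. Keep the pooled column as planned, and say that it describes TDF-based treatment with permitted add-on.
2. Define actual treatment and study drug for the safety analyses.
3. Classify each AE and laboratory abnormality by treatment at onset: TDF alone, TDF plus added NA, or off treatment. Use the recorded medication and dosing dates (Listings 3.1.2 and 3.2.1). State how short interruptions and restarts of TDF after observation are classified.
4. Show the three periods with person-time beside the pooled column in Tables 5.1.1 to 5.1.3.2 and 5.3.3. Note that a subject can contribute to more than one period, so subject counts need not sum to the pooled count.
5. State when the treatment-emergent window ends, and reconcile it with the treatment period in Protocol 8.3.5.2.

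The cost is one derived period flag and extra columns; no new data collection should be needed. The add-on and off-treatment columns will be small, selected on virological or serological outcome, and drawn from later follow-up. They should be read descriptively and not compared formally with TDF alone.

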5. STUDY ENDPONITS

5.1 Primary endpoint

The primary endpoint is the proportion of subjects with serum HBV DNA <20 IU/mL at week 144.

5.2 Secondary endpoints

- The proportion of subjects with virological response (serum HBV DNA <20 IU/mL and serum HBV DNA <69 IU/mL, respectively) at week 48 and 96.
- The proportion of subjects with virological response (serum HBV DNA <20 IU/mL and serum HBV DNA <69 IU/mL, respectively) at week 48, 96 and 144 in the subgroup with confirmed multi-drug resistance at baseline.
- The log₁₀ reduction in serum HBV DNA at Week 48, 96 and 144.
- For HBeAg positive subjects: the proportion of subjects achieving HBeAg loss, HBeAg seroconversion or HBsAg loss and HBsAg seroconversion at Week 48, 96 and 144.
- For HBeAg negative subjects: the proportion of subjects achieving HBsAg loss and HBsAg seroconversion at Week 48, 96 and 144.
- The proportion of subjects with ALT normalization at Week 48, 96 and 144 in subjects who have abnormal ALT at baseline.
- Incidence of subjects who experience viral breakthrough (defined as 1 log increase in HBV DNA from nadir determined by two sequential HBV DNA measurements) up to week 144.
- Subject safety as determined by adverse events and laboratory assessments.

5.3 Exploratory endpoints

- Evaluate the impact of the baseline host and virological characteristics (HBV DNA level, resistance type, HBeAg status, prior treatment with ADV, prior treatment with ETV, prior treatment with IFN, overall duration of prior NA treatment, compliance, cirrhosis, ALT level, age, gender, BMI, AST, r-GT, platelets, INR, total bilirubin, albumin, etc.) and early HBV DNA suppression on response to TDF at week 144.
- Time to virological response to TDF (defined as HBV DNA <20 IU/mL) for overall and subjects with different patterns of mutation.

6. STATISTICAL CONSIDERATIONS

6.1 General rule

All analysis will be conducted using SAS® Version 9.2 or higher (SAS Institute, Cary, NC). For Continuous variables, descriptive statistics will be presented as the mean, standard deviation, minimum, median, maximum, and the number of observations. For categorical variables, the number and percentage for each of the categories will be presented. Counts that are zero will be displayed as "0". Unless otherwise specified, the denominator for all percentages will be based on the number of subjects in the analysis set of that treatment group. Baseline is defined as the last assessment before administration of the study drug.

6.2 Data handling

Missing data can have an impact upon the interpretation of the trial data. In general, values for missing data will not be imputed unless otherwise specified.

All serum HBV DNA results below the lower limit of detection (<20 IU/mL) or results of "not detected" will be analyzed as being the value of the lower limit of quantification, which is 20 IU/mL. For the primary endpoint analyses and other analyses of response (success, failure) at a particular time point, a discontinued subject was considered as "failure" for all efficacy responses post termination. And the missing values of categorical efficacy endpoints (success, failure) will be imputed as "failure" at the analysis visits.

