#### 201215

- 1 All results to be obtained before baseline visit.
- 2 No more than 6 days before or 6 days after the date scheduled based on the time from baseline visit not from the previous visit.
- 3 Demographic data includes birth date, gender and race
- 4 Medical history will include any acute and chronic medical conditions including prior surgery, information related to hepatitis B history, any current and prior HBV medications, and previous HBV-related procedures.
- 5 Update any new medical conditions and/or concomitant medications that have occurred since study screening.
- 6 Concomitant medications including traditional Chinese medicines and/or herbal remedies.
- 7 At screening, a complete physical examination will be performed. For all following indicated visits, a brief physical examination will be performed.
- 8 Including blood pressure, pulse, respiratory rate and temperature.
- 9 Urine pregnancy test will be performed at screening, baseline and every 3 months after dosing.
- 10 Tests will be performed at central lab.
- 11 B ultrasound examination include liver, pancreas, spleen, gall bladder and kidney.
- 12 Urinalysis: urine glucose, ketones, specific gravity, blood, pH and protein.
- 13 HBV DNA will be tested using Roche COBAS Taqman HBV test (LLD:20IU/ML).
- 14 Resistance surveillance will be performed at baseline or under the condition defined in protocol by direct sequencing of the polymerase gene. See Section 6.2.5
- 15 Each study visit: All study medication to be collected and reconciled.

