## 8.3.5. Key Elements of Analysis Plan

Missing data can have an impact upon the interpretation of the trial data. In general, values for missing data will not be imputed unless otherwise specified.

All serum HBV DNA results below the lower limit of detection will be analysed as being the value of the lower limit of detection.

For the primary analysis of HBV DNA<20IU /ml at Week 144, data from non-completers will be considered to be "failures".

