7.4.1 Analysis of primary variable

The primary efficacy endpoint for this study is the proportion of subjects with serum HBV DNA <20 IU/mL at week 144. Primary efficacy endpoints are evaluated by count and percentage, and two-sided 95% CI will also be provided based on normal approximation and continuity correction.

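### The rule that sets every HBV DNA result below 20 IU/mL to 20 IU/mL is not limited to continuous summaries and, taken literally, contradicts the strict <20 IU/mL definition of response

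*SAP*

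**What the plan says.** SAP 6.2 (Data handling) covers "All serum HBV DNA results below the lower limit of detection (<20 IU/mL) or results of" not detected, and says that these "will be analyzed as being the value of the lower limit of quantification, which is 20 IU/mL". Protocol 8.3.5 has a matching rule: "All serum HBV DNA results below the lower limit of detection will be analysed as being the value of the lower limit of detection". Protocol Table 1, footnote 13, gives that limit: "HBV DNA will be tested using Roche COBAS Taqman HBV test (LLD:20IU/ML".

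SAP 5.1 defines the endpoint: "The primary endpoint is the proportion of subjects with serum HBV DNA <20 IU/mL at week 144". SAP 7.4.1 repeats the strict inequality and adds that a "two-sided 95% CI will also be provided based on normal approximation and continuity correction". SAP 7.4.2 uses the same cut-off by visit and in subgroups, alongside a second cut-off of <69 IU/mL. SAP 7.4.3 uses <20 IU/mL as the event for time to response and models HBV DNA negativity at week 144 by logistic regression.

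The only other rules in SAP 6.2 that decide response concern discontinued subjects and missing values. Both are counted as failures.

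**The concern.** The assay floor and the responder cut-off are the same number, and the cut-off is a strict inequality. Replacing a censored result by the floor is a normal device for means and log10 changes, but it cannot also feed a flag that asks whether the value lies under the floor. The rule speaks of all results and stands under general data handling. Nothing in the two documents says that response is read from the laboratory report before the substitution is made.

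No hypothesis is tested in this trial, so the week 144 proportion and its interval are the primary result. If the written rule cannot be followed as it stands, whoever programs the flag must choose a repair that the plan does not contain, and the possible repairs do not all give the same endpoint.

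**Working it through.** **1. The plan's own figure.** Inputs from Protocol 8.2.1 and SAP 3.2: assumed response p = 0.80, margin e = 0.06, 95% confidence (Protocol Table 2), dropout 15%.

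- N = p(1−p)(z/e)² = 0.80 × 0.20 × (1.96/0.06)² = 170.7. The plan states 170.
- Half-width at N = 170: 1.96 × √(0.16/170) = 0.0601, or 6.0 points, as stated.
- Enrolment: 170/0.85 = 200, as stated.

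The sample size reproduces and is not in dispute.

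**2. The rule followed by the flag.** Let x be the reported result and y the analysis value.

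- If x is under 20 or not detected, then y = 20. Otherwise y = x, which is at least 20.
- So y ≥ 20 for every subject with a result, and the condition y < 20 is never met.
- The literal <20 IU/mL count is 0, whatever the data. The <69 IU/mL count is unaffected, because 20 < 69.

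**3. How many subjects this touches at week 144.** The 80% is set against 170 evaluable subjects, and Protocol 8.3.5 and SAP 6.2 count non-completers as failures.

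- Suppressed subjects: 0.80 × 170 = 136.
- mITT proportion: 136/200 = 68%.
- 95% interval by normal approximation: 0.68 ± 1.96 × √(0.68 × 0.32/200) = 0.68 ± 0.0646, or 61.5% to 74.5%. With the continuity correction of 0.5/200 = 0.0025, it is 61.3% to 74.7%.
- Taken literally, the same data give 0/200. The standard-error term vanishes and the interval shrinks to 0 ± 0.25 points.

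**4. The candidate repairs.**

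| Derivation of response | Reported <20 or not detected | Quantified at exactly 20 | Quantified above 20 |
|---|---|---|---|
| Substitute, then test <20 (literal) | no | no | no |
| Substitute, then test ≤20 | yes | yes | no |
| Test the reported result, then substitute | yes | no | no |

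Only the last row matches the stated endpoint in every column. The last two rows differ by the number k of results quantified at exactly 20 IU/mL, which shifts the mITT rate by k/200, or 0.5 points per subject. The documents give no value for k.

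**5. Reach.** The conflict applies to the primary endpoint in mITT and PP, response by visit, the multi-drug-resistance and prior-treatment subgroups, the week 144 logistic regression if negativity means <20 IU/mL, and the Kaplan-Meier, log-rank and Cox analyses.

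**The case against.** The best defence is that nobody would apply the rule this way. The endpoint is defined on serum HBV DNA, which is a measurement and not a substituted value. SAP 6.2 itself labels the results to be substituted as <20 IU/mL, which is the responder condition. The next sentence of SAP 6.2 opens a separate rule for success and failure, and names only discontinuation and missing values as failure. Elsewhere the documents treat <20 and ≥20 IU/mL as complementary observed results (Protocol 3.1), call the outcome negativity (Protocol 8.3.5.1, SAP 7.4.3) and plan on 80% response. A 0% rate would also reveal itself early: SAP 3.1 plans outputs at the 48-week and 96-week cut-offs, and SAP section 9 marks the response tables by visit for the annual report.

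Most of this stands. It shows what was probably intended, and it makes a reported 0% unlikely. It does not supply the missing rule. No passage says that the flag comes before the substitution. The mock tables are in a separate document that is not available here; they may settle the matter, but that cannot be assumed.

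Two stronger readings are tempting and not supported. A reader might infer that the trial will report no responders, but that outcome follows only from literal application. A reader might also put the number affected at 160 of 200 (0.80 × 200). That would require the dropouts to have suppressed week 144 results, whereas the plan sets 80% against 170 evaluable subjects and counts non-completers as failures.

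**Conclusion.** Wrong as written: a stated derivation rule conflicts with the primary endpoint. About 136 of 200 mITT subjects (68%) would fall under the conflict at week 144. That figure rests on the plan's 80% assumption, 15% dropout and non-completers counted as failures.

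The practical effect is modest. The literal result would very likely be caught, and what remains is the risk of an undocumented repair chosen after data have been seen. A ≤20 repair would add 0.5 points to the mITT rate for each result quantified at exactly 20 IU/mL. Because the documents do not say how many such results to expect, a material bias cannot be claimed. The design, the sample size and the use of 20 IU/mL in log10 summaries are not affected.

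**What to change.** Amend SAP 6.2 before database lock, and before any week 48 or week 96 output not yet produced:

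- Limit the substitution of 20 IU/mL to continuous HBV DNA summaries: log10 level, log10 reduction, and the nadir used for breakthrough.
- State that every <20 IU/mL response flag (primary, by visit, subgroups, logistic regression, time to response) is derived from the reported laboratory result before substitution. A report of <20 or not detected is response; any quantified value of 20 or more is no response. The existing failure rules for missing and discontinued subjects stay as they are.
- Use one term for the 20 IU/mL limit. SAP 6.2 calls it both the limit of detection and the limit of quantification, while the protocol uses only the former.

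The cost is a sentence or two and a check that the table shells and programs agree. No new data and no change to the sample size are needed.
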